6.1.4. Adjustment for Covariates

The baseline ECOG status (0, 1, and 2) which was used as the stratification factor will be included as a covariate in relevant statistical modeling for data from Part 2.

6.2. Analysis Methods

6.2.1. Patient Disposition

A summary table will be generated to provide the following by study part, as appropriate:

- Number of patients screened
- Number and percentage of screening failures
- Reason for screening failure
- Number of patients dosed (Part 1 only)
- Number of patients randomized (Part 2 only)
- Number of patients randomized and not dosed (Part 2 only)
- Number of patients dosed and not randomized (Part 2 only)

A separate table will be presented to show the patients included in each analysis set and reason for exclusion from an analysis set.

Patient status at treatment and study completion will be listed and summarized. The listing will include whether patients discontinued from the treatment and the reasons for the discontinuation, along with the date of first and last dose and the date of completion or discontinuation from the treatment. The same information will be provided for patients who discontinued from the study. The following summaries will be added to the disposition table:

- End of treatment status (discontinued study drug or continue on study drug)
- Number and percentage of patients in the FAS who discontinued study drug
- Number and percentage of patients in the FAS who discontinued study drug before 6 cycles
- Number and percentage of patients in the FAS who discontinued study drug after 6 cycles
- Reason for study drug discontinuation
- End of study status (discontinued study or continue in the survival follow-up)
- Number and percentage of patients in the FAS who discontinued the study
- Reason for study discontinuation
- Death and reason for death

6.2.2. Demographic and Other Baseline Characteristics

Demographic and other baseline characteristics, such as age at informed consent date, age groups (18-65, >65-75, >75), race, ethnicity, gender, height, body weight, ECOG status (0, 1, and 2), smoking history (never smoker, former smoker and current smoker, smokeless tobacco, etc), and BMI will be summarized and listed.

6.2.3. Disease Characteristics and Prior Therapies

Disease characteristics including confirmation of diagnosis using neuroendocrine markers (Yes or No) and weight loss in the 6 months prior to randomization (Yes or No, if Yes, $\leq 5\%$ or $>5\%$), will be summarized and listed. Family history of cancer and age at initial diagnosis of lung cancer will be listed only.

The prior anti-cancer therapies, such as prior systemic anti-cancer therapy (Yes or No), prior anti-cancer surgery (Yes or No, and if Yes, related to lung cancer), and prior radiotherapy (Yes or No), will be summarized and listed.

6.2.4. Medical History

Medical history will be coded to SOC and PT using MedDRA Version 20.1.

The number and percentage of randomized patients with any past medical history within each SOC and PT will be provided. A patient will only be counted once within a particular SOC (PT) even if he/she has multiple conditions/diseases in the same SOC (PT). The conditions/diseases from medical history are those conditions/diseases that stopped prior to the study entry.

6.2.5. Concomitant Medications

All medication verbatim terms collected will be coded to Anatomical Therapeutic Classification (ATC) and PT using the WHO-DD Version Sep2017.

Prior medications are defined as those taken by the patient prior to the administration of study drug. Concomitant medications are defined as those taken by the patient at any time between the date of study drug administration and study completion/discontinuation. Medication with start date/time being partially or completely missing will be assumed to be concomitant if it cannot be definitely shown that the medication did not occur during the treatment period.

Medications with onset/end dates that are partially/completely missing will be imputed as follows:

(i) For onset date:

- If only the day part of the medication onset date is missing and occurs in the same month and year as the first dose date of study drug, the date of first dose of study drug will be used as the onset date of the medication. Otherwise, the first day of the month will be used to complete the onset date of the medication;
- If the day and month parts of medication onset date are missing and occur in the same year as the first dose of study drug, the date of the first dose of study drug will be used as the onset date of the medication. Otherwise, January 1st will be used to complete the onset date of the medication;
- If the medication onset date is completely missing, the date of the first dose of study drug will be used as the onset date of the medication.

(ii) For end date:

- If only the day part of the medication end date is missing, the last day of month will be used to complete the end date of the medication;
- If the day and month parts of medication end date are missing, December 31st will be used to complete the onset date of the medication;
- If the medication end date is completely missing and the onset date of the medication occurs after the date of the first dose of study drug, the last date during the treatment period will be used as the medication end date. Otherwise, the date of the first dose of study drug will be used as the medication end date.

Concomitant medications will be summarized by presenting the number and percentage of patients by PT and ATC. Patients taking the same medication multiple times will only be

counted once for that PT or ATC. Each summary will be ordered by descending order of incidence of ATC class and PT within each ATC class.

All prior and concomitant medications will be presented in a patient listing.

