## **Part 2**

In Part 2, eligible patients will be randomized (1:1 fashion) to G1T28 or placebo administered IV once daily on Days 1 to 3 of E/P therapy. Randomization will be stratified by Eastern Cooperative Oncology Group (ECOG) performance status (0 to 1 versus 2). There will be no inpatient dose modifications of G1T28 in Part 2 of the study.

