### **8.6. Prior and Concomitant Medications and Procedures**

All concomitant medications including prescription medications, over-the-counter preparations, growth factors, blood products, and parenteral nutrition taken during the 14 days before the date of enrollment, during the study treatment, and through 30 days after the last dose of study drug will be documented. Documentation will include information regarding start and stop dates, dose(s), and reasons for the medication use.

Administration of other concomitant nonprotocol anticancer therapies prior to progression is not permitted while on this study.

Administration of other concomitant investigational agents for any indication is not permitted while on this study.

Concomitant radiation therapy treatment for SCLC will be regarded as disease progression, and is not permitted while on this study.

Caution should be exercised when administering etoposide phosphate with drugs that are known to inhibit phosphatase activities (eg, levamisole hydrochloride). Although carboplatin has limited nephrotoxic potential, caution should be exercised when administering carboplatin with aminoglycosides, which has resulted in increased renal and/or audiologic toxicity. Any medication that is contraindicated when using etoposide or carboplatin is not permitted, and special warnings and precautions for use of carboplatin and etoposide should be observed.

Necessary supportive care such as antiemetics, antidiarrheals, etc., per the standard of care at the study center will be permitted. **Administration of hematopoietic growth factors in Cycle 1 will not be permitted (ie, no growth factors should be used prior to the actual Cycle 2 Day 1 dosing visit).** However, hematopoietic growth factors may be utilized in subsequent cycles at the investigator's discretion as stated in Section 8.4.4.2. To reduce potential immune system interactions, the use of dexamethasone as an antiemetic should be minimized where possible.

G1T28 is a time-dependent inhibitor of CYP3A4 and is a substrate for CYP3A4. G1T28 exposure may be altered by concomitant use of drugs that are strong CYP3A inhibitors or inducers. The exposure of drugs that are CYP3A substrates may be altered by concomitant use of G1T28 (Section 4.3.2).

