### **13.1. Sample Size and Power**

The sample size for this study is determined by clinical rather than statistical considerations. Up to 40 patients (open-label, dose-finding cohort[s] and an open-label, expansion cohort) will be enrolled in Part 1 of the study and 70 patients will be enrolled in Part 2 of the study (randomized). With 35 patients, the precision for point estimates in each arm is as follows: the 95% confidence interval (CI) width for binary endpoints based on Wilson score intervals are at most the observed proportion  $\pm 0.157$ . The 95% CI width for continuous endpoints using the t-distribution are the observed mean  $\pm 0.344$ \*standard deviation of the endpoint.

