dates of administration of any IV antibiotic overlap with any dates between the start of cycle and end of cycle, that cycle will be considered as having an IV antibiotic administered. Data handling conventions for missing start and stop dates are described in [Section 6.2.5](#).

For the treatment period, the total number IV antibiotics administration is the total number of cycles where IV antibiotics were administered. If a patient did not have any IV antibiotic use, the value of 0 will be assigned to that patient. The number of cycles where IV antibiotics were NOT given is calculated as total number of treatment cycles received – total number of cycles where IV antibiotics were administered.

Therefore, any occurrence of an IV antibiotics administration during the treatment period is defined as a binary variable (Yes or No); Yes if total number of cycles with IV antibiotics administration ≥ 1 is observed, No for other scenarios.

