5.1.1.7. Infection SAEs and Pulmonary Infection SAEs

Each infection SAE and pulmonary infection SAE is captured in the electronic database. The event terms are coded using the MedDRA Version 20.1. The criterion for identifying the proper infection SAE and pulmonary infection SAEs records is as follows: if the system organ class (SOC) from MedDRA takes value “INFECTIONS AND INFESTATIONS”, the preferred term (PT) takes values from [Table 4](#), and the AE is a serious event.

Table 4 PT List for Grouping Infection AEs and Pulmonary Infection AEs

Category	Preferred terms	
Pulmonary Infection AEs	Bronchitis	
	Influenza	
	Pneumonia	
	Pneumonia bacterial	
	Respiratory tract infection	
	Upper respiratory tract infection	
	Viral upper respiratory tract infection	
Infection AEs	Anal abscess	Oral herpes
	Bacteraemia	Pharyngitis streptococcal
	Bronchitis	Pneumonia
	Candida infection	Pneumonia bacterial
	Chronic sinusitis	Respiratory tract infection
	Conjunctivitis	Sepsis
	Infection	Skin infection
	Influenza	Upper respiratory tract infection
	Nasopharyngitis	Urinary tract infection
	Oral candidiasis	Urosepsis
		Viral upper respiratory tract infection

A cycle is considered to have an infection SAE if any date between the start and stop date of the AE overlaps with any date between the start of cycle and end of cycle. If an event ends on the

cycle start day, it will not be counted as an event in that cycle unless the event also started on that day. For the treatment period, the total number of infection SAE events is the number of cycles where at least one infection SAE is observed. If a patient did not have any infection SAE events, the value of 0 will be assigned to that patient. Data handling conventions for missing start and stop dates for AEs are described in [Section 5.2.1](#).

Any occurrence of an infection SAE during the treatment period is defined as a binary variable (Yes or No); Yes if total number of infection SAE events ≥ 1 is observed, No for other scenarios.

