5.2. Safety Endpoints

5.2.1. Adverse Events (AEs)

All AEs will be coded from verbatim text to PTs and grouped by SOC using the MedDRA Version 20.1. AEs will be collected from the time of signature of informed consent throughout the treatment period and including the post-treatment visit. AEs are graded by investigator according to CTCAE, Version 4.03.

Any AE that started on or after the first dose of study drugs and up to the last dose +30 days will be included as a treatment-emergent AE (TEAE). AEs with an unknown/not reported onset date will also be included.

Other AE variables include drug-related AEs, AEs leading to study drug discontinuation or study withdrawal, AEs leading to death, SAEs.

AEs with onset/end dates that are partially/completely missing will be imputed as follows:

(i) For onset date:

- If only the day part of the AE onset date is missing and occurs in the same month and year as the first dose date of study drug, the date of first dose of study drug will be used as the onset date of the AE. Otherwise, the first day of the month will be used to complete the onset date of the AE;
- If the day and month parts of the AE onset date are missing and occur in the same year as the first dose of study drug, the date of the first dose of study drug will be used as the onset date of the AE. Otherwise, January 1st will be used to complete the onset date of the AE;
- If the AE onset date is completely missing, the date of the first dose of study drug will be used as the onset date of the AE.

(ii) For end date:

- If only the day part of the AE end date is missing, the last day of the month will be used to complete the end date of the AE;
- If the day and month parts of the AE end date are missing, December 31st will be used to complete the end date of the AE;
- If the AE end date is completely missing and the onset date of the AE occurs after the date of the first dose of study drug, the last date during the treatment period +30 days will be used as the AE end date. If the AE end date is completely missing and the onset date of the AE occurs prior to the date of the first dose of study drug the date of the first dose of study drug will be used as the AE end date.

AEs related to hematologic toxicity will be pooled based on the preferred MedDRA Version 20.1. [Table 10](#) outlines those terms that will be consolidated.

Table 10 Preferred Terms to Be Consolidated

Presented term in the table	Preferred Term
Neutropenia	Neutropenia

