All statistical tests will be conducted at a two-sided significance level of 20% unless otherwise specified. For Part 2 data, the G1T28 + E/P therapy will be compared to the placebo + E/P therapy group. Where appropriate, model-based point estimates, together with their 80% CIs will be presented along with the two-sided p-values for the tests. P-value will be presented to 4 decimal places, if the p-value <0.0001, the value will be presented as “<0.0001”.

For continuous data, the same number of decimal places as in the raw data will be presented when reporting mean, median, minimum and maximum; one more decimal place than in the raw data will be presented when reporting SD and standard error (SE). The derived variables will be presented with 1 decimal place. Percentages will be reported with 1 decimal point; if the count is

0, no percentage will be presented. Value of percentage less than 1% will be presented as “<1%.” Value of percentage less than 100% but $\geq 99.5\%$ will be presented as “>99%.”

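### G-CSF, ESA and IV antibiotic endpoints count pre-dose records that only reach Cycle 1 Day 1, and the infection SAE endpoints do not require onset after the first dose

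*SAP*

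**What the plan says.** **Medication endpoints.** SAP 5.1.1.6 marks a cycle as having IV antibiotic use if any "dates of administration of any IV antibiotic overlap with any dates between the start of cycle and end of cycle". SAP 5.1.1.4 (G-CSF) and 5.1.1.5 (ESA) use the same test. None of the three requires that use began on or after the first dose. One such cycle makes the patient a yes for the whole treatment period.

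**Cycle start and missing end dates.** SAP section 5 starts each cycle with study drug on Day 1. SAP 6.2.5 gives a medication with a completely missing end date the last date of the treatment period if it began after the first dose. For all others: "Otherwise, the date of the first dose of study drug will be used as the medication end date".

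**AE endpoints.** SAP 5.1.1.7 also starts from overlap: "A cycle is considered to have an infection SAE if any date between the start and stop date of the AE overlaps" with a date in the cycle. It then drops an event that ends on the cycle start day unless it also began that day, and SAP 5.1.1.1 does the same for febrile neutropenia. SAP 5.2.1 defines a treatment-emergent event ("Any AE that started on or after the first dose of study drugs", up to 30 days after the last dose), but neither 5.1.1.1 nor 5.1.1.7 invokes that definition.

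**Pre-dose records exist.** Protocol 8.6 documents prescription medications, and also "growth factors, blood products, and parenteral nutrition taken during the 14 days before the date of enrollment". AEs are collected from consent.

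**The concern.** The SAP handles one situation in two ways. An AE that reaches only the first day of a cycle is not attributed to that cycle; a medication that does so is. For medications the imputation rule creates the overlap by itself: a record with no evidence of use after dosing is given the one end date that guarantees it is counted.

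G-CSF, ESA and IV antibiotic use are prospectively defined endpoints in SAP Table 3. SAP 6.2.7.1 compares them between arms with p-values, under the general rule: "All statistical tests will be conducted at a two-sided significance level of 20% unless otherwise specified". Events fixed before randomized treatment could begin carry no information on treatment. At 35 patients per arm, a few of them are visible in a proportion.

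**Working it through.** **1. Inputs and the plan's own figures.** Protocol 13.1 gives 70 patients in Part 2, and allocation is 1:1, so there are 35 per arm. With n = 35, the Wilson 95% half-width at p = 0.5 is 0.1572, and t(0.975, 34 df)/√35 = 0.3435. Both agree with the stated 0.157 and 0.344. The plan states no power, event rate or pre-dose medication rate.

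**2. The date rules applied to test records** (Day 1 = first dose; Cycle 1 = Days 1 to 22):

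| Start | End | G-CSF, ESA, IV antibiotic | Infection SAE |
|---|---|---|---|
| Day −7 | Day −1 | not counted | not counted |
| Day −7 | Day 1 | **counted** | not counted |
| Day −7 | missing, imputed to Day 1 | **counted** | not counted |
| Day −7 | Day 4 | counted | **counted** |
| missing, imputed to Day 1 | missing | counted | counted |
| Day 5 | Day 8 | counted | counted |

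Rows 2 and 3 are the medication defect. Row 4 is the infection SAE gap. Row 5 matters for the fix: an onset imputed to the first dose looks like a start on Day 1.

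Partial end dates add to this. SAP 6.2.5 and 5.2.1 move an end date with only the day missing to the end of the month. A record that stopped earlier in the dosing month can then be carried past Day 1, for medications and AEs alike.

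**3. Size per patient.** The endpoints are ever/never, so a miscounted record changes the result only if the patient has no later event. One such patient moves an arm by 1/35 = 2.9 points; a net imbalance of two moves the difference by 2/35 = 5.7 points.

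**4. Size in the comparison (assumed values).** Let b be the share of each arm with a counted pre-dose record and p the true on-treatment rate. The observed rate is p + b(1−p), so with equal b the difference shrinks by the factor (1−b). For p = 0.30 and 0.10 with b = 0.05: 0.30 + 0.05×0.70 = 0.335 and 0.10 + 0.05×0.90 = 0.145, a difference of 0.190 instead of 0.200.

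Approximate power at two-sided 20%, n = 35 per arm:

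| b | 30% vs 10%: difference | power | 40% vs 20%: difference | power |
|---|---|---|---|---|
| 0 | 0.20 | 0.80 | 0.20 | 0.71 |
| 5% | 0.19 | 0.72 | 0.19 | 0.66 |
| 10% | 0.18 | 0.66 | 0.18 | 0.61 |
| 20% | 0.16 | 0.55 | 0.16 | 0.53 |

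These use an unstratified normal approximation, not the planned stratified exact CMH test. The chance difference in b between arms has SD √(2b(1−b)/35): 0.052 at b = 5% and 0.072 at b = 10%. It reaches the observed difference multiplied by about (1−p).

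**The case against.** The strongest reply is that the endpoint is utilization during the treatment period. A course begun two days before dosing and continued to Day 10 is use in that period, and counting only new starts answers a different question. That stands. The clear misclassification is limited to records that merely end on Day 1, in fact or by imputation; a new-start count belongs in a sensitivity analysis.

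The entry and conduct rules also limit exposure. Protocol 7.1.2 excludes prior SCLC chemotherapy and serious active infection, Protocol 10.3 lets only patients who still meet eligibility start Cycle 1, and Protocol 8.6 bars growth factors until Cycle 2 Day 1 dosing. Growth-factor carry-over and ongoing infection SAEs should therefore be uncommon. IV antibiotics are less constrained: the criteria do not mention them, and the infection exclusion does not define serious.

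Stronger readings are tempting, but the documents do not support them:

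- A reader might infer that every record touching Day 1 counts, infections included. Infection SAEs that end on Day 1 are dropped, and so are those that began before dosing and have a completely missing end date.
- A reader might extend the point to transfusions. SAP 5.1.1.2 and 5.1.1.3 count transfusions that fall within a cycle, apply no start/stop overlap rule and do not refer to 6.2.5. A transfusion dated before Day 1 is outside Cycle 1.
- A reader might conclude that entry needs a washout. The 14 days in Protocol 8.6 is a recording window, and the counting defect can be removed without changing eligibility.
- A reader might suspect bias toward one arm. Part 2 is randomized and blinded, and the rules are the same in both arms.

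**Conclusion.** The point holds in its limited form. As written, SAP 5.1.1.4 to 5.1.1.6 with 6.2.5 always score a pre-dose medication with no end date as treatment-period use, and score one that ended on Day 1 the same way. SAP 5.1.1.7 can count an infection SAE that began before dosing, but only if its recorded or imputed end falls after Day 1.

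The expected consequence is a diluted and noisier Part 2 comparison, mainly for IV antibiotics. The firm figure is 2.9 points per misclassified patient with no later event. The power losses rest on assumed event rates and on carry-over shares of 5% to 20%, for which the documents give no support; at the low end the difference moves only from 0.20 to 0.19. The case for correction rests on the rule being wrong as written and cheap to repair, not on a demonstrated large effect.

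**What to change.** Before unblinding, amend the SAP as follows.

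(a) In 5.1.1.4 to 5.1.1.6, do not count in a cycle a medication record that ends, or is imputed to end, on that cycle's start day unless it also started that day. This copies the rule in 5.1.1.1 and 5.1.1.7.

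(b) In 5.1.1.1 and 5.1.1.7, count only treatment-emergent AEs as defined in 5.2.1. State whether that definition's upper limit is also meant to apply: with a last dose on Day 3 it falls on Day 3 + 30 = 33, while the last cycle runs to Day 36.

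(c) List medication use that began before the first dose and continues past Day 1. As a sensitivity analysis, repeat the G-CSF, ESA and IV antibiotic comparisons counting only use started on or after the first dose. Flag records whose onset was imputed to the first-dose date, because they would pass that filter.

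No new imputation rule is needed, nor any change to transfusion scoring or eligibility. The cost is minor programming on data already collected, one listing and three repeated comparisons.
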